## **6.3. Data Handling**

### **6.3.1. Baseline Values**

Baseline values are defined as the last value (using fasting blood sample values for lipoprotein and plasma glucose) prior to administration of investigational product on Day 1 (predose).

### **6.3.2. Missing Data**

Primary analysis of efficacy endpoints will utilize observed data only; missing values will not be imputed. A sensitivity analysis using a last observation carried forward (LOCF) approach may be considered. If performed, the LOCF imputation will replace any missing value from a DB post-Baseline visit with the last available non-missing value from a DB post-Baseline visit.

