## **4. STUDY DESIGN AND PLAN**

This is a Phase 2, double-blind, randomized, placebo-controlled, multicenter study, evaluating the effects of OCA, and the subsequent addition of statin therapy, on lipoprotein metabolism in subjects with NASH with fibrosis stage 1 to 4, but no evidence of hepatic decompensation, in the DB phase, followed by an open-label LTSE phase to evaluate long term safety and efficacy.

Approximately 80 subjects with histological evidence of definite or probable NASH, who meet all inclusion and none of the exclusion criteria will be enrolled in the study. The histological evidence of definite or probable NASH will be based on the central read of a liver biopsy obtained no more than 1 year prior to randomization and a nonalcoholic fatty liver disease activity score (NAS) of 4 or greater. Subjects not using statin therapy (ie, statin-free) and statin-treated subjects may be enrolled. Statin-treated subjects will be required to stop statin treatment (after signing informed consent) for up to 5 weeks, including a 4-week statin washout period, prior to Randomization/Day 1.

Subjects will have a screening period of up to 5 weeks prior to Randomization/Day 1. At the Randomization (Day 1) Visit, subjects will be randomized in a 1:1:1:1 ratio to receive OCA 5 mg, OCA 10 mg, OCA 25 mg, or placebo, orally, once daily, for 16 weeks. Randomization will be stratified by the pre-randomization fasting serum LDLc ( $\leq$ 125 mg/dL or  $>$ 125 mg/dL) and baseline fibrosis stage (stage 1, 2 or stage 3, 4).

[figure not shown]
Subjects will attend on-site clinic visits at Weeks 2, 4, 8, 12, and 16 and will be contacted at Weeks 6, 10 and 14 to assess safety and treatment compliance. At the Week 4 Visit, all subjects will initiate treatment with atorvastatin at a dose of 10 mg once daily. At the Week 8 Visit, atorvastatin will be increased to 20 mg once daily (if 10 mg daily is tolerated), and continued for an additional 4 weeks. After 4 weeks of treatment at 20 mg, the atorvastatin dose may be titrated (up or down) as clinically indicated. The final visit during the DB phase will occur at Week 16, after which subjects may continue into the open-label LTSE.

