## **9. EFFICACY ANALYSES**

The primary and secondary efficacy analyses will be based on the EE Population. Analyses on the ITT Population will only be performed if greater than 20% of ITT subjects are excluded in the EE Population. All analyses are to be carried out on observed data, as there are no imputations planned. The efficacy data are a result of the centralized, specialized nuclear magnetic resonance (NMR) lipoprotein assay and the central laboratory serum chemistry. All analyses of lipoprotein metabolism will include fasted samples only. For all lipoprotein concentration values, the serum chemistry panel results will be used. For particle size and particle concentration, the NMR lipoprotein assay results will be used. Sensitivity analysis may be performed with the NMR lipoprotein concentration results.

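### The optional LOCF rule has no treatment-phase limit, so an ITT run could enter pre-atorvastatin LDLc values as Week 16 results and bias each arm's estimated change upward

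*SAP*

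**What the plan says.** Section 6.3.2 bases the primary efficacy analysis on observed data: "missing values will not be imputed". It then adds an option: "A sensitivity analysis using a last observation carried forward (LOCF) approach may be considered". If that option is used, "the LOCF imputation will replace any missing value from a DB post-Baseline visit with the last available non-missing value" from a double-blind post-Baseline visit. The rule has no limit by visit or by treatment period.

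Section 9 reads differently: "All analyses are to be carried out on observed data, as there are no imputations planned". Appendix A lists ITT tables and ITT repeated-measures (MMRM) tables for LDL, but no LOCF table.

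The treatment schedule is in Section 4. "Subjects will attend on-site clinic visits at Weeks 2, 4, 8, 12, and 16". "At the Week 4 Visit, all subjects will initiate treatment with atorvastatin at a dose of 10 mg once daily". At Week 8 there is a planned increase, subject to tolerability. The primary endpoints (Section 3.1) are change and percentage change to Week 16 in LDLc, LDL particle size and LDL particle concentration.

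Section 9.1 commits to two sensitivity analyses for the primary endpoint, both in the ITT Population: the by-visit ANCOVA of Section 6.2.3 and the repeated-measures ANCOVA of Section 6.2.4.

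**The concern.** LOCF assumes that the last value seen is a fair stand-in for the missing one. Here the design changes treatment in every arm between the early visits and the endpoint visit. A Week 2 value, and a Week 4 value drawn before the first atorvastatin dose, reflects OCA or placebo alone. The Week 16 value is meant to reflect OCA or placebo plus atorvastatin. Part of the primary objective (Section 2) is to see how atorvastatin modifies the OCA effect, and a value carried from before atorvastatin cannot show that.

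The SAP recognises the two periods elsewhere: Section 11.2 repeats the adverse-event summaries for events with onset before atorvastatin starts. The LOCF rule makes no such separation.

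What is at stake is a sensitivity table that disagrees with the primary result because of how it was built, not because of the missing data it was meant to probe.

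**Working it through.** **1. The plan's own figure.** Section 5 assumes a 22 mg/dL LDLc increase, SD 24, 20 subjects per group and a two-sided 0.05 level, and states power above 97.3%. A one-sample t-test on change from Baseline has noncentrality 22/24 × √20 = 4.10 on 19 degrees of freedom, which gives 97.29%. The figure is reproduced as a within-group calculation (a two-sample t-test would give 80.6%). The quantity the trial is sized on is therefore an arm's own change from Baseline, which is also what Section 9.1 estimates first. Comparisons with placebo are labelled exploratory there.

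**2. Which carried values come from before atorvastatin.**

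| Last LDLc available | Treatment at that sample | Treatment planned at Week 16 |
|---|---|---|
| Week 2 | OCA or placebo alone | plus atorvastatin |
| Week 4, drawn before the first atorvastatin dose | OCA or placebo alone | plus atorvastatin |
| Week 8 or 12 | plus atorvastatin, possibly at another dose | plus atorvastatin |

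Only the first two rows cross the start of atorvastatin. That the Week 4 sample precedes the first dose is the natural reading, but the SAP does not state it.

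**3. Where the rule can act.** The EE Population requires completion of the double-blind phase (Section 7.4), and Section 8.1 defines completion by non-missing LDL assessments at the scheduled visits, Week 16 included. An EE subject therefore has no missing Week 16 LDL value to fill. The effect at Week 16 arises only in an ITT run.

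**4. Size within an arm.** Let p be the share of an arm whose Week 16 value is carried from before atorvastatin. Let D be the pre-atorvastatin change minus the change those subjects would have shown on atorvastatin at Week 16. For the unadjusted arm mean:

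LOCF mean = (1 − p) × on-atorvastatin change + p × pre-atorvastatin change, so shift = p × D.

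The SAP gives neither a dropout rate nor an atorvastatin effect, so both are assumed:
- p = 5%, 10% or 20% (1, 2 or 4 of 20).
- The pre-atorvastatin change is taken as Section 5's +22 mg/dL for OCA 25 mg. The on-atorvastatin Week 16 change is assumed to lie between 0 and −30 mg/dL. Hence D = 22 − 0 = 22 up to 22 − (−30) = 52 mg/dL.

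| p | D = 22 | D = 52 |
|---|---|---|
| 5% | 1.1 | 2.6 |
| 10% | 2.2 | 5.2 |
| 20% | 4.4 | 10.4 |

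(upward shift in the arm mean, mg/dL)

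The yardstick is the arm standard error, 24/√20 = 5.4 mg/dL, borrowing Section 5's SD. The shift runs from 1.1/5.4 = 0.2 to 10.4/5.4 = 1.9 standard errors.

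**5. Size between arms.** With the same D in both arms, the contrast shifts by (pA − pB) × D. It is zero for equal p. For an illustrative 20% against 5%, it is 0.15 × 22 = 3.3 to 0.15 × 52 = 7.8 mg/dL.

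**6. After the change.** If LOCF is dropped, or may carry only on-atorvastatin values, the shift from Week 2 and Week 4 values is zero. The repeated-measures model fits a separate mean for each treatment at each week, so it does not place an early value at Week 16.

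**The case against.** The best defence is that nothing the SAP commits to is affected. LOCF is optional, Section 9 says no imputation is planned, Appendix A has no table for it, and Section 9.1 already names the repeated-measures ITT analysis. Section 6.2.8 also calls the study descriptive, so no formal decision would rest on an LOCF table. All of this stands, and it limits the weight of the point. It does not make the rule sound. The text fixes how LOCF would be done if chosen and gives no condition for choosing it, so the choice could follow sight of the data.

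A reader might infer more: that OCA-related withdrawal would make LOCF create or inflate a dose-related LDLc rise. The documents do not support that. The SAP gives no dropout rate, overall or by arm. Its plan to summarise discontinuations due to pruritus shows that these are foreseen, not that they will differ by dose before Week 8. All arms, placebo included, start atorvastatin at Week 4, so equal early dropout and an equal D leave the contrasts about unbiased.

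A reader might also express the shift as a percentage of the 22 mg/dL in Section 5. That figure is a change without atorvastatin, not the Week 16 effect on atorvastatin, so the percentage would not be a share of the endpoint at issue.

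Lastly, being on atorvastatin at Week 16 is the plan and not a certainty, since Section 8.1 provides for summarising atorvastatin discontinuation.

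**Conclusion.** The point holds as a defect in an optional ITT sensitivity analysis. Run as worded, the rule would mix two treatment periods at Week 16. If atorvastatin lowers LDLc, it would overstate each arm's change by p × D, even with equal dropout across arms. Under the assumed ranges (p of 5–20%, D of 22–52 mg/dL) that is about 1–10 mg/dL, or 0.2 to 1.9 arm standard errors. With no early dropout it is zero. Both ranges are assumptions, D starts from the OCA 25 mg planning value, and the formula is for unadjusted means.

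Bias in the arm contrasts or the dose-trend test is conditional on early dropout or D differing by arm, and is not shown. The primary observed-data EE analysis is not affected. Sections 6.3.2 and 9 also need to agree on whether any imputation is foreseen.

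**What to change.** Delete the LOCF option from Section 6.3.2. This also brings it into line with Section 9. State in Sections 6.3.2 and 9.1 that the ITT repeated-measures ANCOVA of Section 6.2.4 is the missing-data sensitivity analysis for the primary endpoints.

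If LOCF is kept, add that no value is carried across the start of atorvastatin, so that only values taken on atorvastatin can fill later visits. Also say when the analysis will be run, and amend the sentence in Section 9 to match.

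The cost is SAP wording only. The model and its ITT tables are already planned, and neither sample size nor data collection changes.

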### **6.3.3. Partial Dates**

If only a partial date is available and is required for a calculation, the following standards will be applied:

- Diagnosis date (eg, NASH diagnosis date)
  - For missing day only: Day will be imputed as the first day of the month (ie, 01).

- For missing day and month: Day and month will be imputed as the first day of the year (ie, 01 January).
- Start dates (eg, AE onset date or start date of medication)
  - For missing start day only: Day will be imputed as the first day of the month (ie, 01) with the following exception: if the partial date falls in the same month and year as the date being used in the calculation (eg, first dose date, informed consent date), then the partial date will be imputed to equal the date being used for the calculation.
  - For missing start day and month: Day and month will be imputed as the first day of the year (ie, 01 January) with the following exception: if the partial date falls in the same year as the date being used in the calculation (eg, first dose date, informed consent date), then the partial date will be imputed to equal the date being used for the calculation.
  - For missing start day, month, and year: Date will be imputed to the date being used in the calculation (eg., first dose date, informed consent date).
  - Imputed start dates must be prior to the stop date.
- Stop dates (eg, AE resolution date or stop date of medication)
  - For missing stop day only: Day will be imputed as the last day of the month (ie, 28, 29, 30, or 31).
  - For missing stop day and month: Day and month will be imputed as the last day of the year (ie, 31 December).
  - For missing stop day, year, and month: Date will be imputed as date of completion or discontinuation in the DB phase.
  - Imputed dates should not extend beyond the date of completion or discontinuation of the DB phase.
  - Imputed stop dates must be on or after the start date.

#### **6.3.4. Data Conventions**

Unless otherwise specified, in summary tables of continuous variables, the minimum and maximum values will be displayed to the same number of decimal places as the raw data, the mean, median, and IQR will be presented to 1 extra decimal place compared to the raw data, and the SD, SEM, LS Mean, and CIs will be displayed to 2 extra decimal places compared to the raw data. Coefficient of variation will be displayed with one decimal place.

The concentration versus time data as reported by the respective bioanalytical laboratory should be used without rounding for all analyses. The bioanalytical generated tables should not be reported to any greater accuracy than that of the concentration data. Default significant figures used for bioanalytical tables is three significant figures, with exception to time related parameters which will be reported as two decimal places.

Rounding will only occur after all calculations have been incorporated. For tables where rounding is required, rounding will be done to the nearest round-off unit; for example, when rounding to the nearest integer, values  $\geq XX.5$  will be rounded up to  $XX + 1$  (eg, 97.5 will round up to 98), whereas values  $< XX.5$  will be rounded down to  $XX$  (eg, 97.4 will round down to 97).

Percentages based on frequency counts will be based on available data, and denominators will generally exclude missing values unless some form of imputation is defined or a ‘missing’ category is presented. For frequency counts of categorical variables, categories with zero counts will be displayed for the sake of completeness. For example, if none of the subjects discontinue due to “lost to follow-up,” this reason will be included in the table with a count of zero.

Percentages based on frequency counts will be presented as a whole number (no decimal places), and values less than 1% will be presented as “<1%.” Values less than 100% but that round up from 99.5% to 100% will be presented as “>99%.”

### 6.3.5. Standard Calculations

Variables requiring calculation will be derived using the following formulas:

- **Days:** A duration expressed in days between one date (*date1*) and another later date (*date2*) will be calculated using the following formulas:

$$\text{duration in days} = \text{date2} - \text{date1} + 1, \text{ where } \text{date2} \geq \text{date1}$$

$$\text{duration in days} = \text{date2} - \text{date1}, \text{ where } \text{date2} < \text{date1}$$

- **Months:** A duration expressed in months is calculated as the number of days divided by 365.25 / 12.

- **Years:** A duration expressed in years between one date (*date1*) and another date (*date2*) is calculated using the following formulas:

$$\text{duration in years} = (\text{date2} - \text{date1} + 1)/365.25, \text{ where } \text{date2} \geq \text{date1}$$

$$\text{duration in years} = (\text{date2} - \text{date1})/365.25, \text{ where } \text{date2} < \text{date1}$$

- **Age:** Age is calculated as the number of years from the date of birth (DOB) to the specified date, eg, date of informed consent (DOIC). If the month of DOIC < month of DOB or the month of DOIC=DOB and the day of DOIC < day of DOB, then the following formula is used:

$$\text{age (years)} = \text{year of DOIC} - \text{year of DOB} - 1$$

Otherwise, the following formula is used:

$$\text{age (years)} = \text{year of DOIC} - \text{year of DOB}$$

- **Height:** Height measured in inches (in) are converted to centimeters (cm) using the following formula:

$$\text{height (cm)} = \text{height (in)} \times 2.54$$

- **Weight:** Weight measured in pounds (lb) are converted to kilograms (kg) using the following formula:

$$\text{weight (kg)} = \text{weight (lb)} / 2.2046$$

- **Temperature:** Temperature measured in degrees Fahrenheit are converted to degrees Celsius using the following formula:

$$\text{temp (degrees Celsius)} = 5 / 9 \times (\text{temp [degrees Fahrenheit]} - 32)$$

- **Body Mass Index (BMI):** BMI is calculated using height (cm) and weight (kg) using the following formula:

$$\text{BMI (kg/m}^2\text{)} = \text{weight (kg)} / ([\text{height (cm)} / 100]^2)$$

- **Change from Baseline:** Change from Baseline is calculated as:

$$\text{change from Baseline} = \text{post-Baseline value} - \text{Baseline value}$$

- **Percentage Change from Baseline:** Percentage change from Baseline is calculated as:

$$\text{percentage change from Baseline} = 100 \times ([\text{post-Baseline value} - \text{Baseline value}] / \text{Baseline value})$$

- **Geometric Mean:** In order to calculate a geometric mean and corresponding 95% CI, the following steps are used:

- Transform the data by taking natural logarithms ( $\log_e$ )
- Calculate the mean and 95% CI of the  $\log_e$ -transformed data
- Exponentiate the mean and the lower and upper CIs back to the original scale in order to obtain the geometric mean and corresponding 95% CI.

The geometric coefficient of variation (geometric CV%) is calculated as  $100 \times \sqrt{e^{\text{SD}^2} - 1}$  where SD is the SD of the  $\log_e$ -transformed data.

- **Coefficient of Variation** - The coefficient of variation (CV%) will be calculated as the ratio of the standard deviation to the arithmetic mean using the following formula:

$$\text{Coefficient of variation} = \frac{\text{standard deviation}}{\text{arithmetic mean}}$$

### 6.3.6. Cardiovascular Risk Scores Calculations

Cardiovascular risk scores (ie, FRS and Reynolds) will be calculated at the time of data analysis using data collected via the Baseline Tobacco Use, Family Cardiovascular History eCRFs, and the central laboratory data. The calculations are as follows:

#### FRS:

The 10-year cardiovascular disease risk (%) for women =  $[1 - 0.95012^{\exp(B - 26.1931)}] \times 100\%$ , where

$B = 2.32888 \times \text{natural logarithm (age)} + 1.20904 \times \text{natural logarithm (total cholesterol)} - 0.70833 \times \text{natural logarithm (high-density lipoprotein cholesterol)} + 2.76157 \times \text{natural logarithm (systolic blood pressure if not treated)} + 2.82263 \times \text{natural logarithm (systolic blood pressure if treated)} + 0.52873 \text{ (if current smoker)} + 0.69154 \text{ (if diabetic)}$

The 10-year cardiovascular disease risk (%) for men =  $[1 - 0.88936^{\exp(B - 23.9802)}] \times 100\%$ , where  $B = 3.06117 \times \text{natural logarithm (age)} + 1.2370 \times \text{natural logarithm (total cholesterol)} - 0.93263 \times \text{natural logarithm (high-density lipoprotein cholesterol)} + 1.93303 \times \text{natural logarithm (systolic blood pressure if not treated)} + 1.99881 \times \text{natural logarithm (systolic blood pressure if treated)} + 0.65451 \text{ (if current smoker)} + 0.57367 \text{ (if diabetic)}$  [Framingham Heart Study 2016].

#### Reynolds Score:

The 10-year cardiovascular disease risk (%) for women =  $[1 - 0.98634^{\exp(B - 22.325)}] \times 100\%$ , where

$B = 0.0799 \times \text{age} + 3.137 \times \text{natural logarithm (systolic blood pressure)} + 0.180 \times \text{natural logarithm (high-sensitivity C-reactive protein)} + 1.382 \times \text{natural logarithm (total cholesterol)} - 1.172 \times \text{natural logarithm (high-density lipoprotein cholesterol)} + 0.134 \times \text{hemoglobin A1c (\%)} \text{ (if diabetic)} + 0.818 \text{ (if current smoker)} + 0.438 \text{ (if family history of premature myocardial infarction)}$  [Ridker, 2007].

The 10-year cardiovascular disease risk (%) for men =  $[1 - 0.8990^{\exp(B - 33.097)}] \times 100\%$ , where

$B = 4.385 \times \text{natural logarithm(age)} + 2.607 \times \text{natural logarithm(systolic blood pressure)} + 0.963 \times \text{natural logarithm(total cholesterol)} - 0.772 \times \text{natural logarithm(high-density lipoprotein cholesterol)} + 0.405 \text{ (if current smoker)} + 0.102 \times \text{natural logarithm(high-sensitivity C-reactive protein)} + 0.541 \text{ (if parental history of premature myocardial infarction)}$  [Ridker, 2008].

#### 6.3.7. Fibrosis Scores Calculations

Fibrosis scores (ie, NFS and APRI) will be calculated at the time of data analysis using data collected via the Medical History eCRF and the central laboratory data. The calculations are as follows:

**NFS** =  $-1.675 + 0.037 \times \text{age (years)} + 0.094 \times \text{BMI (kg/m}^2\text{)} + 1.13 \times \text{impaired fasting glucose(fasting glucose} \geq 110 \text{ mg/dL) / diabetes (yes = 1, no = 0)} + 0.99 \times \text{AST/ALT ratio} - 0.013 \times \text{platelets (}\times 10^9/\text{L)} - 0.66 \times \text{albumin (g/dL)}$

**APRI** =  $((\text{AST(IU/L)}/\text{AST upper limit of normal}) / \text{platelets (}\times 10^9/\text{L)}) \times 100$

**FIB-4** =  $(\text{Age (years)} \times \text{AST(IU/L)}) / (\text{Platelets}(\times 10^9/\text{L}) \times \text{sqrt(ALT(IU/L))})$

**BARD** score is calculated by designating 0 to 2 points to the following parameters:  $\text{BMI} \geq 28 \text{ kg/m}^2 = 1 \text{ point}$ ,  $\text{BMI} < 28 \text{ kg/m}^2 = 0 \text{ point}$ ;  $\text{AST/ALT ratio} \geq 0.8 = 2 \text{ points}$ ,  $\text{AST/ALT ratio} < 0.8 = 0 \text{ point}$ ; freshly recognized or preexisting diabetes mellitus type 2 = 1 point. A total of 2 to 4 points indicates significant fibrosis.

#### 6.3.8. Anomalous Concentration Handling

Anomalous concentration values are those that, after verification of bioanalytical validity, are grossly inconsistent with the known or expected pharmacokinetic behavior of the drug. If an entire profile appears inconsistent with those of other subjects or previous periods, then the clinical pharmacologist/pharmacometrist will use her/his discretion regarding the handling of this data. The rationale will be documented within the CSR. Any such anomalous concentration data will also be identified in the relevant tables or as a stand-alone table of the CSR.

## 7. ANALYSIS POPULATIONS

### 7.1. Randomized Population

### 7.2. Intent-to-Treat (ITT) Population

All randomized subjects who receive any amount of investigational product within the DB phase will be included in the ITT Population. Treatment assignment will be based on the randomized treatment allocation.

